8.2 Trial procedures

At V1 (Day -90 to -1), the volunteers' eligibility is assessed according to the pre-specified inclusion/exclusion criteria and the informed consent is obtained. The medical history, vital signs (including BMI) are taken, physical and eye examinations are performed. Refer to Table 3 for eye examination method required at V1. Concomitant medications (CM) and AEs are recorded. Blood samples for screening of hepatitis B and C, HIV, syphilis and safety biochemistry/haematology are drawn. Urine is collected for pregnancy test and PCR for *C. Trachoma* and gonorrhoea infections.

At V2 (Day 0), the inclusion/exclusion criteria are assessed again. Eye and symptom-direct physical examination are performed and vital signs are taken. Refer to Table 3 for eye examination method required at V2. Any AEs and CMs are reviewed and recorded. Urine is collected for pregnancy test. The volunteers are randomised according to the randomisation scheme via the eCRF. Before the 1st IM vaccination, blood samples for safety and immunogenicity determination (please refer to type of tests in Table 4) are drawn and ocular samples are taken. The volunteers (hereafter subjects) receive the 1st IM vaccination. The subjects are observed for any immediate AE for 60 minutes after the vaccination. The diary card is issued with instructions before discharge from the site.

At V3 (Day 14), the diary card is collected and reviewed. Adverse events and CM are reviewed and recorded. Vital signs are taken and symptom-directed physical examination is performed as necessary. Blood samples for safety and immunogenicity (please refer to type of tests in Table 4) are drawn.

At V4 (Day 28), the AEs and CM are reviewed and recorded. Vital signs are taken. Eye and symptom-directed physical examinations are performed. Refer to Table 3 for eye examination method required at V4. Before the vaccinations, blood samples for safety and immunogenicity determination (please refer to type of tests in Table 4) are drawn, and urine for pregnancy and ocular samples are taken. The subjects receive the 2nd IM vaccinations together with ID or TO vaccination as specified in the Figure 1. In the event that the first TO vaccinations are planned for several subjects on the same day, there should be a minimum of two hours between the TO dosing for each subject. The two hour lagging between the TO doses should be performed for the first five subjects receiving TO doses and can be discontinued after the first these five subjects if there are no safety concerns. The subjects are observed for any immediate AE for 60 minutes after the vaccination. The diary card is issued with instructions before discharge from the site.

At V5 (Day 42), the diary card is collected and reviewed, AEs and CM are reviewed and recorded. Vital signs and ocular samples are taken. Eye and symptom-directed physical examination are performed. Refer to Table 3 for eye examination method required at V5. Blood samples for safety and immunogenicity (please refer to type of tests in Table 4) are drawn.

At V6 (Day 56), the AEs and CM are recorded. Eye and symptom-directed physical examination are performed. Refer to Table 3 for eye examination method required at V6. Blood samples for immunogenicity determination are drawn (please refer to type of tests in Table 4). Ocular sample is taken.

At V7 (Day 112), the AEs and CM are recorded. Vital signs are taken. Eye and symptom-directed physical examinations are performed. Refer to Table 3 for eye examination method required at V7. Before the vaccinations, blood samples for safety and immunogenicity determination (please refer to type of tests in Table 4) are drawn, and urine for pregnancy and ocular samples are taken. The subjects receive the 3rd IM vaccinations together with ID or TO vaccination as specified in the Figure 1. The subjects are observed for any immediate AE for 60 minutes after the vaccination. The diary card is issued with instructions before discharge from the site.

At V8 (Day 126), the diary card is collected and reviewed. The AEs and CM are recorded. Vital signs are taken, eye and symptom-directed physical examination are performed. Refer to Table 3 for eye examination method required at V8. Blood samples for safety and immunogenicity determination (please refer to type of tests in Table 4) are drawn. Ocular sample is taken.

At V9 (Day 140), the AEs and CM are recorded. Vital signs are taken. Eye and symptom-directed physical examinations are performed. Refer to Table 3 for eye examination method required at V9. Before the vaccinations, blood samples for safety and immunogenicity determination (please refer to type of tests in Table 4) are drawn, urine for pregnancy and ocular sample are taken. The subjects receive the final vaccination with a TO CTH522 (or placebo) boost as specified in the Figure 1. The subjects are observed for any immediate AE for 60 minutes after the vaccination. The diary card is issued with instructions before discharge from the site.

At V10 (Day 143), the diary card is reviewed. The AEs and CM are recorded. Vital signs are taken. Eye and symptom-directed physical examination are performed. Refer to Table 3 for eye examination method required at V10. Ocular sample is taken.

At V11 (Day 154), the diary card is collected and reviewed, AEs and CM are recorded. Vital signs are taken. Eye and symptom-directed physical examinations are performed. Refer to Table 3 for eye examination method required at V11. Blood samples for safety and immunogenicity determination (please refer to type of tests in Table 4) are drawn and ocular sample is taken.

V12 (Day 238) is the end-of-trial visit. The AEs and CM are reviewed and recorded. Vital signs are taken. Eye and physical examinations (including symptom-directed) are performed. Refer to Table 3 for eye examination method required at V12. Urine is collected for pregnancy and PCR for *C. Trachoma* and gonorrhoea infection test. Blood samples for safety and immunogenicity determination (please refer to type of tests in Table 4) are drawn and ocular sample is taken.

8.3 Trial population and planned number of subjects

The trial plans to screen approximately 110 subjects with the aim to randomise 66 subjects. The enrolled subjects will be healthy males and females aged 18–45 years.

8.3.1 Inclusion criteria

- IC1: Healthy males and females between 18–45 years old on the day of the first vaccination

- IC2: Has been properly informed about the trial and signed the consent form
- IC3: Is willing and likely to comply with trial procedures
- IC4: Is prepared to grant authorised persons access to his/her trial-related medical record
- IC5: Is willing to use acceptable contraceptive measures during the trial (two weeks before and two weeks after the trial). Heterosexually active female capable of becoming pregnant must agree to use hormonal contraception, intrauterine device, intrauterine hormone-releasing system, or to complete abstinence from at least two weeks before the first vaccination until at least two weeks after the last. Complete abstinence (defined as refraining from heterosexual intercourse) must be in line with the preferred and usual lifestyle of the subject. Periodic abstinence (e.g. calendar, ovulation, symptothermal, post-ovulation methods), withdrawal and progestogen-only oral hormonal contraception where inhibition of ovulation is not the primary mode of action are not acceptable methods of contraception

8.3.2 Exclusion criteria

General

- EX1: Is positive for *C. trachomatis* via urine PCR or has a known history of *C. trachomatis*
- EX2: Is positive for gonorrhoea via urine PCR test, or HIV, hepatitis B/C, syphilis via blood tests
- EX3: Has a significant active disease such as cardiac, liver, immunological, neurological, psychiatric or clinically significant abnormality of haematological or biochemical parameters
- EX4: Has BMI $\geq 35 \text{ kg/m}^2$
- EX5: Is currently participating in another clinical trial with an investigational or non-investigational drug or device, or was treated with an investigational drug within 28 days before the first vaccination
- EX6: Has received, or plans to receive, any immunisation within 14 days of the start of the trial or during the trial immunisations
- EX7: Is currently receiving treatment with systemic immunosuppressive agents. Topical steroids are allowed unless applied to the IM or ID injection site
- EX8: Has a condition which in the opinion of the investigator is not suitable for participation in the trial
- EX9: Is known or confirmed to have allergy to any of the vaccine constituents

- EX10: Is unable to refrain from use of contact lenses. Contact lenses should be avoided two days before TO administration and for seven days later (longer if any ongoing local eye AE)
- EX11: Has any evident ocular disease upon eye examination (prior to first vaccination) or any medical history of ocular disease that, in the opinion of the investigator, may impact the subject's participation in the trial

Female-specific

- EX12: Is pregnant (positive pregnancy test) or breastfeeding or not willing to use contraception during the trial
- EX13: Has confirmed history of pelvic inflammatory disease or significant gynaecological diseases

8.4 Randomisation procedure

The randomisation will be performed via the eCRF system at the site. Randomisation data is kept strictly confidential, accessible only to authorised persons, until the time of unblinding. Only when the trial has been completed or for expedited purpose, and the database has been locked, the codes will be broken and made available for data analysis.

8.5 Blinding and unblinding

Blinding will be obtained by shielding the subjects from seeing the preparation of the trial drug and by having unblinded trial personnel not involved in any trial assessments (immunogenicity or safety) responsible for preparing and administering the trial drug. This unblinded staff will prepare and administer trial drug, and be the only ones doing IMP accountability.

During vaccination, the blinded staff will be shielded from seeing trial drug or any procedures related hereto. This blinded staff will observe the subject and monitor any AEs during or after vaccination.

All used material will be removed by the unblinded staff without revealing the identity of the fluid. The IMP accountability will be monitored by an unblinded clinical research associate (CRA).

The PI and delegates at the site will have access via the IBM Clinical Development trial database to unblind individual subjects and obtain information on trial drug administered in case of a medical emergency. The investigator should only unblind the treatment allocation to a subject during the clinical trial if it is relevant to the safety of the subject. The identity of the IMP would be revealed by the PI or designee for that subject only.

It may be necessary for the CRO to unblind a subject's treatment for expedited reporting to the Competent Authorities (CA) and/or Research Ethic Committee (EC). In these situations, the CRO will keep the unblinding from the PI, site staff, subject, and SSI personnel involved in monitoring, data analysis and interpretation. In cases of suspected unexpected adverse reactions (SUSAR), the unblinding will be known to the safety manager at SSI.

Unblinding of a subject is performed in the IBM Clinical Development trial database and is only possible for persons who have obtained rights to perform unblinding. The date of unblinding, reason and the person performing the unblinding are saved via an audit trail.

A screen-dump of the unblinding page including the information of the unblinded subject, the reason for unblinding, date and person performing the unblinding, is made and printed. This print is filed in an envelope with the subject's allocation number and sealed with a label and kept in a secure at the site.

The IBM Clinical Development system has an up-time of more than 99%, so system-down is a small risk. In case of system-down, a designated person at [REDACTED], who is not otherwise involved in any trial-related work, can be contacted to obtain information of the trial drug allocated to any specific subject.

Subjects with unblinded treatment allocation will not be withdrawn and will not be replaced.

8.6 Immunogenicity assessments

The immunogenicity objective, *anti-CTH522 IgG*, will be determined using ELISA at SSI.

The immunogenicity will further be analysed using a panel of exploratory assays performed at SSI and ICL as outlined in Table 4. The serum IgA ELISA + anti-CTH522 IgG subtypes + neutralising antibody test for the mucosal immune response, whereas the ocular anti-CTH522 IgG + IgA ELISA test the immune response in the eye. The T- and B-cell Elispot and ICS flow using frozen PBMCs assess the cell-mediated immunity. The transcriptional analysis consists of taking PBMCs and re-stimulating *in vitro* with CTH522. The aim is to identify gene transcription profiles associated with Th17 T-cells, Th1, and Th2 in the different active vaccine groups.

Table 4: Safety and immunogenicity assessments

Laboratory tests	Analysed at:	Medium, amount and unit	Visit	1	2	3	4	5	6	7	8	9	10	11	12
			Day	-	0	14	28	42	56	112	126	140	143	154	238
Safety															
Safety lab	ICHT	Blood 1 x 13 (8) ml		13	8	8	8	8		8	8	8		8	8
Immunogenicity															
Serum IgG ELISA ¹	SSI	Blood 1 x 10 ml			10	10	10	10	10	10	10	10		10	10
Serum IgA ELISA+ anti- CTH522 IgG subtypes + neutralising antibodies ²	SSI	Blood 1 x 10 ml			10	10	10	10	10	10	10	10		10	10
T- and B-cell Elispot frozen PBMCs ²	T-cell: SSI B-cell: ICL	Blood in heparin tube 5 x 6 ml			30	30	30	30	30	30	30	30		30	30
ICS flow frozen PBMCs ²	ICL	Blood in heparin tube 5 x 6 ml			30	30	30	30	30		30	30		30	30
Transcriptional analysis frozen PBMCs ²	SSI	Blood in heparin tube 2 x 6 ml			12						12			12	
Total blood collection															
For immunogenicity					92	80	80	80	80	50	92	80		92	80
For safety				13	8	8	8	8		8	8	8		8	8

ICHT=Imperial College Healthcare NHS Trust; ICL=Imperial College London; ICS=intracellular cytokine staining; PBMC=peripheral blood mononuclear cell; SSI=Statens Serum Institut

¹for secondary endpoints

²for exploratory endpoints

8.7 Safety assessments

The trial staff must record all AEs, non-serious and serious, expected and unexpected in the relevant form of the eCRF. This starts from the time after the subject has signed the informed consent form (ICF) at V1 until the end-of-trial at V12.

The source of AEs covers, for example, the subject's response to questions about his/her health (a standard non-leading question), information from diary card, symptoms spontaneously reported by a subject, results from pre-defined laboratory testing and examinations where the findings are assessed by the investigator to be clinically significant changes or abnormalities, and other information relating to the subject's health becoming known to the investigator (for example hospitalisation).

The subjects will remain at the site for 60 minutes after each vaccination so that any immediate AEs observed may be recorded. It is also documented if no immediate AEs occurred. Trial staff will ensure that the subjects have a diary card, ruler to measure and thermometer to enable them to record AEs while away from the clinical site.

From the day of vaccination until seven days later, solicited AEs and unsolicited AEs will be recorded through the use of diary cards. Between Day 7–14, the subject will be asked to fill in details in the diary *only* if they experience an AE or if any medications were taken.

8.8 Predetermined reasons for discontinuation

The trial may be terminated at any time if participation in the trial is no longer considered safe by the PI, the sponsor or the regulatory authorities.

A subject is free to discontinue from the trial at any time without giving a reason. The investigator may at any time withdraw a subject if his/her participation is no longer considered safe or relevant. The date and reason (if given) for discontinuation must be recorded in the eCRF. In the case of pregnancy and/or anaphylactic reactions, the subject must be withdrawn. In case of an identified pregnancy, the pregnancy form(s) is to be used. If a subject for any reason leaves or is withdrawn from the trial or has a significant protocol deviation, he/she will not be replaced if the subject has received at least one trial vaccination.

Because the healthy subjects gain no benefit from participation in the trial, dosing in the trial must be stopped if:

- there is one or more subjects with SAEs considered to be related to the IMP
- there are two or more subjects with a severe AE considered to be at least possibly related to the IMP (based on the judgement of the investigator)
- there are two or more subjects with clinically significant AEs considered to be at least possibly related to the IMP (based on the judgement of the investigator) and which are

deemed to have impacted to a significant degree on the safety or physical or mental integrity of the affected subject(s), or which have resulted in permanent discontinuation of dosing in the affected subject(s)

8.9 Contraindications

8.9.1 Temporary contraindications

The below conditions (events) are considered temporary contraindications to the trial products and are assessed before each vaccination is administered.

- Oral temperature $> 38.3^{\circ}\text{C}$ measured immediately before each vaccination
- Acute illness as judged by the investigator
- Antipyretics used on the day of vaccination
- Systemic treatment with immunosuppressive agents
- Ongoing conjunctivitis or similar on the day of TO administration

If the subject is experiencing one of the above conditions, the vaccination must be postponed until he/she has recovered. On the rescheduled visit, the subject should be checked for the above temporary contraindications. If the subject is found to be eligible, the vaccine can be administered while maintaining the planned intervals.

8.9.2 Permanent contraindications

If the subject experienced the following events or received the following medication, he/she must be withdrawn from the trial:

- acute anaphylactic reaction after administration of any of the trial vaccines
- ocular disease

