- Cohort E will receive three IM vaccinations of 85 µg CTH522-CAF09b. The rationale for the A and E cohorts is to investigate the impact of the adjuvant on the immunogenicity results.
- Cohort F will receive only placebo in form of 0.9% NaCl (IM, ID and TO).

Figure 1: Trial diagram

IM=intramuscular injection with CTH522-CAF01 or CTH522-09b 85 µg or 15 µg; ID=intradermal injection with non-adjuvanted CTH522 24 µg; TO=topical ocular with non-adjuvanted CTH522 12 µg in each eye

Table 3: Trial flow chart

Trial visit (V)	1	2	3	4	5	6	7	8	9	10	11	12
Trial day	-	0	14	28	42	56	112	126	140	143	154	238
Windows (days)	-90 to -1	0	V2 + 12-16	V2 + 26-30	V4 + 12-16	V4 + 26-30	V4 + 77-91	V7 + 12-16	V7 + 26-30	V9 + 2-4	V9 + 12-16	V9 + 91-105
Informed consent	X											
Med. hist+demographics	X											
In-/exclusion criteria	X	X										
Blood for hep B and C, HIV, syphilis	X											
PCR for C. Trachoma and gonorrhoea infection ¹	X											X
Urinary pregnancy test	X	X		X			X		X			X
Physical examination	X											X
Eye exam including retina*	X*				X			X			X	
Eye exam**	X	X		X	X	X	X	X	X	X	X	X
Record weight/height	X											
Vital signs ²	X	X	X	X	X		X	X	X	X	X	X
Concomitant medication	X	X	X	X	X	X	X	X	X	X	X	X
Randomisation		X										
Vaccination and route		1 IM		2 IM ID TO			3 IM ID TO		4 TO			
Issue diary card		X		X			X		X			
Review diary card			X		X			X		X	X	
Symptom-directed PE		X	X	X	X	X	X	X	X	X	X	X
Record adverse events	X	X	X	X	X	X	X	X	X	X	X	X
Safety lab ³	X*	X ⁵	X ⁵	X ⁵	X ⁵		X ⁵	X ⁵	X ⁵		X ⁵	X ⁵
Serum IgG ELISA ⁶		X	X	X	X	X	X	X	X		X	X
Serum IgA ELISA+anti-CTH522 IgG subtypes + neutralising ab ⁶		X	X	X	X	X	X	X	X		X	X
Ocular anti-CTH522 IgG + IgA ELISA (strip)		X		X	X	X	X	X	X	X	X	X
T- and B-cell Elispot frozen PBMCs ⁷		X	X	X	X	X	X	X	X		X	X
ICS flow frozen PBMCs ⁷		X	X	X	X	X		X	X		X	X
Transcriptional analysis frozen PBMCs ⁸		X						X			X	
End-of-trial												X

ID=intradermal; IM=intramuscular; PE=physical examination; TO=topical ocular; V=visit

*A biomicroscopy (e.g. via slit lamp examination), examining all areas of the eye including the retina which can be performed by a specialist at an eye clinic. If this procedure cannot be performed at V1, it is acceptable at V2 as long as it is performed prior to the first vaccination.

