### 7.2.1 Adverse Events

The summaries will include number of events, number of subjects, and proportion of subjects reporting these events.

Certain, probable, or possible related AEs are defined as Adverse Drug Reactions (ADRs).

An overall summary table will include summary of TEAEs, TESAEs, Fatal AEs, ADRs, AEs leading to drug withdrawal, drug interruption, or leading to withdrawal from trial, AEs by severity, AEs by relationship, AEs by outcome, and ADRs by severity.

A summary by SOC and PT will be presented for:

- TEAEs
- Serious Adverse Events (SAEs)

- TEAEs by severity (mild, moderate, severe, potentially life-threatening)
- TEAEs by relationship (Certain, probable, possible, not related)
- ADRs by severity
- TEAEs leading to drug interrupted
- TEAEs leading to drug withdrawn
- TEAEs leading to withdrawal

Listings will be made of all AEs, including non-TEAEs, SAEs, clinically significant AEs, ADRs including Suspected Unexpected Serious Adverse Reaction (SUSARs), and TEAEs leading to drug interruption or withdrawal from treatment.

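### Anaphylaxis or ocular disease takes a subject out of the trial, not only off vaccine, so scheduled safety observation ends early in that subject

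*Protocol*

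**What the plan says.** Protocol section 8.9.2 gives two triggers, acute anaphylaxis after any trial vaccine and ocular disease, and one action: "If the subject experienced the following events or received the following medication, he/she must be withdrawn from the trial". Section 8.8 repeats the action for anaphylaxis and adds pregnancy: "In the case of pregnancy and/or anaphylactic reactions, the subject must be withdrawn".

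Elsewhere the plan treats stopping vaccine and leaving the trial as different things:
- The stopping rule in Protocol section 8.8 says "dosing in the trial must be stopped if" certain events occur, and it names a dosing-only outcome for individuals ("permanent discontinuation of dosing in the affected subject(s").
- SAP section 7.2.1 has separate summaries for "TEAEs leading to drug withdrawn" and "TEAEs leading to withdrawal".

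AE recording is planned to V12, Day 238 (Protocol section 8.7). In Table 3 the row "Eye exam including retina" is marked at V1, V5, V8 and V11; the last three come 14 days after the Day 28, 112 and 140 doses. A simpler eye examination is marked at every visit except V3. Safety blood is drawn at V2, V3, V4, V5, V7, V8, V9, V11 and V12. At later dosing visits the draw precedes the dose (section 8.2: "Before the vaccinations, blood samples for safety and immunogenicity determination (please refer to type of tests in Table 4) are drawn"), so it also serves as a late check on the dose before.

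An AE that is open or of unknown outcome at a subject's last visit is followed until resolved or stable (section 10.1.1). Conjunctivitis on a TO dosing day only postpones the dose (section 8.9.1). Exposed subjects who withdraw remain in the SAF (SAP section 4).

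**The concern.** Safety is the primary objective, and ocular reactions after TO dosing are one of the co-primary endpoints. Section 8.9.2 ends participation because of a safety event, so scheduled observation stops in subjects who have already had one. I found no early-withdrawal visit and no visit after withdrawal in either document. Followed as written, nothing is scheduled to look for a second or late-onset event, a laboratory change or a new eye finding in that subject.

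A related anaphylaxis would ordinarily be an SAE and stop dosing trial-wide under section 8.8. That rule stops dosing and does not itself end visits. Unaffected subjects could therefore stay under observation while the affected subject leaves.

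There is also a reporting consequence. SAP section 5.1 allows percentages to use either the analysis set or the subjects with non-missing values. Where the analysis set is used, a withdrawn subject counts as event-free for time that nobody observed.

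**Working it through.** The plan states no figure on this point, so the check is a count from Table 3 (nominal days 0, 14, 28, 42, 56, 112, 126, 140, 143, 154 and 238 for V2 to V12).

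**1. Ocular disease found at the visit 14 days after a Day 28, 112 or 140 dose**

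| Found at | Nominal days to V12 | With windows | Visits left, each with an eye examination | Retinal examinations among them | Safety draws left |
|---|---|---|---|---|---|
| V5 | 238 − 42 = 196 | 178–214 | 7 (V6–V12) | 2 (V8, V11) | 5 (V7, V8, V9, V11, V12) |
| V8 | 238 − 126 = 112 | 101–123 | 4 (V9–V12) | 1 (V11) | 3 (V9, V11, V12) |
| V11 | 238 − 154 = 84 | 75–93 | 1 (V12) | 0 | 1 (V12) |

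Windows: V4 to V12 is 77 + 26 + 91 = 194 to 91 + 30 + 105 = 226 days. Taking off V5 at 12–16 days gives 178–214. V7 to V12 is 26 + 91 = 117 to 30 + 105 = 135, less 12–16 gives 101–123. V9 to V12 is 91–105, less 12–16 gives 75–93.

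**2. The part that does not depend on later doses**

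The totals above include visits that follow doses this subject would not receive. The fairer comparison is time observed after the last dose actually given. A completer has 238 − 140 = 98 days (91–105). The withdrawn subject has 14 (12–16). The shortfall is 98 − 14 = 84 days, range 91 − 16 = 75 to 105 − 12 = 93, and is the same for all three visits. If the disease is found at V12, nothing is lost.

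**3. Anaphylaxis on a dosing day**

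| Dose | Safety draws lost that do not depend on later doses | All scheduled draws left |
|---|---|---|
| Day 0 | V3, V4, V12 = 3 | 8 |
| Day 28 | V5, V7, V12 = 3 | 6 |
| Day 112 | V8, V9, V12 = 3 | 4 |
| Day 140 | V11, V12 = 2 | 2 |

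On the same yardstick the time lost after the last dose is up to 98 nominal days (91–105).

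**4. Which analyses could move in the ocular scenario**

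- The injection-site and systemic Fisher tests use the 14 days after Day 0 (SAP sections 7.1.1 and 7.1.3). That period is over by V5.
- The ocular Fisher tests use the 14 days after Day 28 and after Day 112 (SAP section 7.1.2). On nominal timing the period for the dose just given is complete at V5 or V8; a visit at the early edge of its window would fall two days short. A later period needs a dose that the subject would not receive under either rule.
- What remains is descriptive: other AEs (7.1.4), general AE summaries (7.2.1), vital signs (7.2.2) and the laboratory listing (7.2.3).

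A dosing-day anaphylaxis falls inside a 14-day period, so I make no such statement for that case.

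**5. Weight of one subject**

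Group sizes are in a figure not shown. Assume equal active groups: 0.91 × 66 ≈ 60 subjects (Protocol section 11.4.3), over 10 groups = 6 each. One subject is then 1/36 = 2.8% of pooled Cohorts A–C, 1/12 = 8.3% of Cohort B, or 1/6 = 17% of a single group. With 5 to 7 per group the last figure runs from 1/5 = 20% to 1/7 = 14%. These are one subject over an assumed denominator, not an estimate of bias.

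**The case against.** **The protocol does not say that visits stop.** Correct. That is inferred from withdrawal from the trial together with the absence of any schedule afterwards. If the sponsor means follow-up to continue, a sentence saying so is still needed.

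**Safety cover does not disappear.** This stands and narrows the point. Besides the follow-up of open AEs, section 10 allows unscheduled tests to investigate an AE, and AE sources include spontaneous reports and health information that reaches the investigator. A reader might infer that the triggering event is abandoned or its data lost; the documents show the opposite. None of these provisions schedules a search for something new, however.

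**Every eye complaint would lead to withdrawal.** A reader might infer this because section 8.9.2 does not qualify ocular disease. Section 8.9.1 limits that reading, since conjunctivitis or similar on a TO day only delays the dose. The number of subjects reaching 8.9.2 is probably small.

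**Both triggers are uncommon, and leaving may be kinder to a healthy volunteer.** The protocol calls anaphylaxis very rare, and neither document gives a rate for either trigger. Some immunogenicity visits take about 100 ml of blood (92 + 8 ml in Table 4). Continued follow-up needs only the 8 ml safety draw, so that burden does not have to be carried over.

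**Keeping an undosed subject can distort the tables too.** This also stands. SAP section 7.1.4 anchors AE periods to vaccinations, and SAP section 5 leaves a subject who received less treatment in the assigned cohort. Without a rule, undosed time would be reported under a vaccination that was never given. The change therefore needs a short SAP addition as well as protocol wording.

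**Conclusion.** The point holds as a modest, low-cost improvement. Scheduled detection of new AEs, laboratory changes and eye findings ends with withdrawal. After ocular disease found 14 days after the last dose received, that means 84 fewer nominal days of post-dose observation than a completer has (75 to 93). In that scenario the effect is limited to the individual's safety and the descriptive outputs.

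A reader might infer that the primary safety comparisons are biased. The documents do not support that: no planned Fisher test changes in the ocular scenario, few subjects are likely to be affected, and no conclusion is shown to change. A reader might also extend the figures to pregnancy. Section 8.8 says only that the subject is withdrawn, the pregnancy form is not shown, and visits to V12 would generally not capture birth outcome, so I claim no figure there.

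The conclusion assumes that withdrawal from the trial ends scheduled visits and that no manual outside these two documents says otherwise.

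**What to change.** **Protocol 8.9.2, and 8.8 for anaphylaxis.** Keep both triggers. Replace withdrawal from the trial with *no further trial vaccine*. A consenting subject continues AE recording, eye examinations and 8 ml safety draws at the scheduled visits to V12. A subject who chooses to leave early is offered the V12 safety assessments at that time.

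**SAP 7.1.4.** Add one sentence: AEs after a subject's last dose are counted from that dose, or shown separately, so that undosed time is not reported under later vaccination periods. SAP section 7.2.1 already has a category for AEs leading to the drug being withdrawn.

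**Cost.** The visits are already planned. At £100 per visit (Protocol section 12.1), follow-up after ocular disease at V5, V8 or V11 costs 7 × £100 = £700, 4 × £100 = £400 or 1 × £100 = £100. After a Day 0 anaphylaxis it is at most 10 × £100 = £1,000. All are within the £1,200 maximum. Blood is at most 8 × 8 = 64 ml. The downside is a few visits by subjects who are no longer dosed and a small SAP addition.
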